One major challenge is the delivery of this potential therapeutic CNTF agent to the back of the eye, and in particular, to the retina. The blood-retinal barrier prevents the penetration of a variety of molecules to the neurosensory retina from plasma in a manner similar to the action of the blood-brain barrier, which exists between the central nervous system and systemic circulation. To overcome this challenge, Neurotech Pharmaceuticals (Neurotech) developed

encapsulated cell technology (ECT), and specifically the NT-501 implant, to enable controlled, sustained delivery of therapeutic agents directly into the vitreous humor, thus providing direct access to the retina while restricting exposure of the growth factor outside the eye. ECT utilizes cells encapsulated within a semi-permeable polymer membrane that secretes therapeutic factors directly into the vitreous. Further, ECT devices can be surgically retrieved, providing an added level of safety.

Histopathologic studies of multiple forms of retinal neurodegenerative diseases have demonstrated the efficacy of CNTF as an effective treatment to reduce photoreceptor cell loss. Consequently, the use of the implanted NT-501 device, which secretes CNTF into the vitreous, may be beneficial in people with MacTel. A Phase 1 study is completed although we continue to follow these participants to accumulate further data on the effect of the intraocular NT-501 implant in 7 participants with bilateral MacTel. The primary outcome was the safety of the NT-501 implant and the associated surgical procedure. We found the implanting of the NT-501 was safe as demonstrated by the ERG findings and visual function results as measured by visual acuity and microperimetry (Chew 2015).

2 Background and Rationale

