- To investigate long term safety and efficacy of the NT-501 implant in participants previously enrolled in the NTMT-01 and NTMT-02 protocols.
- To investigate the change in the ellipsoid zone (area of [inner/outer segment] IS/OS loss) in participants previously enrolled in the NTMT-01 and NTMT-02 protocols, as measured by en face imaging by spectral domain optical coherence tomography (SD-OCT) in study eye(s).

5 Study Design and Methods

This is a prospective, multi-center, single-masked, sham-controlled follow-up study of the 7 participants that have completed 60 months of follow up in the open label NTMT-01 study (Cohort 1) and the 66 participants who completed 24 months of follow up in the NTMT-02 study (Cohort 2). All participants will be followed for an additional 48 months. Appendix 1 presents the scheduled examinations during the extended 48 month follow up period.

In the event that the NTMT-02 study is positive, Cohort 2 participants who received sham only may be eligible for active treatment in the control/non-treated eye.

6 Study Conduct

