8.2 Analyses in Support of the Efficacy Outcomes

Cohort 1

For continuous measures mean, median and distribution of change from baseline in BCVA, and enlargement of inner/outer segment discontinuity as measured by SD-OCT will be computed separately for study eyes and fellow eyes. For dichotomous outcomes proportions along with 95% confidence intervals will be computed separately for study eyes and fellow eyes.

Cohort 2

Continuous efficacy measures will be assessed using mixed effects models with an overall Type I error rate of 0.05 (no adjustments of the type I error rate will be made). Due to clustered data (data from two eyes for a percentage of the participants), the variability associated with the estimates of effect (mean difference) from a fixed effects model is likely to be biased, leading to

incorrect test statistics and confidence intervals. For example, if the correlation from paired eyes is ignored, the standard error for the treatment effect is likely to be overestimated when paired eyes from the same participant are in different treatment groups. For this reason, the unpaired t-test for the comparison of means between two treatment groups is not appropriate as it assumes that observations from the same cluster are independent. The appropriate statistical analysis of clustered data should take such correlation into consideration which can be accomplished for continuous outcome measures using a mixed effects model. The mixed effects model will incorporate both random (accounting for the correlation between eyes) and fixed effects (treatment) into the model and will be estimated with accompanying 95% confidence intervals and compared between treatment groups. For dichotomous outcomes, logistic regression incorporating the generalized estimation equation (GEE) methodology with accompanying 95% confidence intervals will be performed to determine if there are significant differences in the odds between the two treatment groups.

The efficacy analyses will be repeated to investigate the strength of potential predictors using multivariable mixed effects models or multiple logistic regression models. Examples of potential predictors include the following: baseline visual acuity, clinical site, participant's age at enrollment and gender.

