8.4 Safety Analysis

Long term safety will be assessed through the summary of ocular and non-ocular adverse events, serious adverse events and pre-specified safety outcome as defined in Section 6.1.3 and will include frequency and descriptive tabulation. No formal statistical analysis will be employed. Safety analyses will include all participants who received the implant or sham.

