8.5 Adverse Events

Adverse events will be tabulated by body system, high-level term and preferred term separately for each Cohort. Summaries of adverse events by severity will be provided. Separate summaries will be prepared for non-ocular and ocular adverse events, with events in the study eye(s) and fellow eye summarized separately for Cohort 1 and 2. Separate summaries of non-

ocular and ocular adverse events reported as related to the implant or the implant surgery will be prepared. Serious adverse events will be summarized similarly. Adverse events leading to discontinuation from the study will be listed and tabulated.

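### Long-term safety is planned as frequencies only: Section 8.4 gives no time at risk and no interval, although time with the implant will differ between participants

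*Combined protocol and SAP*

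**What the plan says.** The first objective in Section 4 is "To investigate long term safety and efficacy of the NT-501 implant in participants previously enrolled in the NTMT-01 and NTMT-02 protocols".

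Section 8.4 covers ocular and non-ocular adverse events, serious adverse events and the outcomes listed in Section 6.1.3. It states that the assessment "will include frequency and descriptive tabulation. No formal statistical analysis will be employed", and that "Safety analyses will include all participants who received the implant or sham".

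Section 8.5 adds detail: "Adverse events will be tabulated by body system, high-level term and preferred term separately for each Cohort". It also plans tables by severity, by relation to implant or surgery, and for study and fellow eyes. It does not say that implant and sham eyes will be shown separately among the Cohort 2 study eyes.

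Intervals appear only for efficacy. For Cohort 1, Section 8.2 states: "For dichotomous outcomes proportions along with 95% confidence intervals will be computed separately for study eyes and fellow eyes".

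Three other provisions make time at risk unequal:
- Section 7.10 allows withdrawal at any time.
- Section 5 allows later implantation of sham-only Cohort 2 participants if NTMT-02 is positive.
- Section 10 invites participants whose device is removed to stay in follow-up.

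Under Section 6.1.3, adverse events are captured from extension consent, and earlier ones become history. Section 6.9 places consent at Visit 1, which is Month 72 in Cohort 1 and Month 36 in Cohort 2.

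**The concern.** A count over everyone treated answers how many had the event. It does not say over how much observation, or how large a risk the data still allow. Both questions matter for a device that stays in the eye for years.

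- **Precision.** With so few eyes, no events or one event is a likely result even when the risk is not small. A bare 0% does not show what has been excluded.
- **Exposure.** Time in the study is not time with an implant. A sham-only participant implanted later has a short exposure, and an explanted participant has follow-up without exposure. Someone who withdraws stops contributing observation but, if kept in the denominator, counts like a completer.
- **Comparison.** Section 7.3 treats a frequency well above known rates as unexpected, and Section 7.8 refers to aggregate comparison with a concurrent or historical control group. Percentages from unequal follow-up are a weak basis for either.

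**Working it through.** The plan states no safety rate, precision or dropout figure, so there is nothing of its own to reproduce.

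**Inputs from the documents**
- Cohort 1: 7 participants, 7 study eyes. Cohort 2: 66 participants, 98 study eyes (Study Summary).
- Adverse-event window: Month 72 to 108 in Cohort 1 and Month 36 to 72 in Cohort 2, about 36 months each (Sections 6.1.3 and 6.9).

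**Assumptions**
- Implanted eyes in Cohort 2. If every participant has one or two study eyes, 98 − 66 = 32 have two and 66 − 32 = 34 have one. With one implant in each two-eye participant and in half of the others, the count is 32 + 17 = 49. Range shown: 32 to 60.
- Yearly risk of 2% or 5%, constant over time.
- Loss of 0%, 10% or 30%, spread evenly over the three years.

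**Step 1. Upper limit when no event is seen.** The exact (Clopper-Pearson) two-sided 95% upper limit for 0 of n is 1 − 0.025^(1/n).

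| Eyes | Upper limit |
|---|---|
| 7 | 41.0% |
| 32 | 10.9% |
| 49 | 7.3% |
| 60 | 6.0% |

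**Step 2. Chance of seeing nothing.** With a true risk of 5%, the chance of no event is 0.95^7 = 0.70 in 7 eyes and 0.95^49 = 0.08 in 49 eyes.

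**Step 3. The same limit as a rate.** With complete follow-up, 7 eyes give 7 × 3 = 21 eye-years. The exact Poisson upper limit for zero events is −ln(0.025)/21 = 3.689/21, or 17.6 per 100 eye-years. For 49 eyes it is 3.689/147, or 2.5 per 100.

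**Step 4. Crude proportion against true three-year risk.** Write r for the yearly risk, F = 1 − (1 − r)^3 for the true risk, and A for the average risk accrued by those who leave, where A = 1 − F/(3 × −ln(1 − r)). If a fraction d leaves and all stay in the denominator, the crude proportion is (1 − d)F + dA and the gap is d(F − A).

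- r = 2%: F = 5.88%, A = 2.97%. At d = 30%, crude = 0.7 × 5.88 + 0.3 × 2.97 = 5.0%, against 5.9%.
- r = 5%: F = 14.26%, A = 7.31%. At d = 30%, crude = 0.7 × 14.26 + 0.3 × 7.31 = 12.2%, against 14.3%.
- At d = 10% the gaps are 0.1 × 2.91 = 0.3 points and 0.1 × 6.95 = 0.7 points.
- At d = 0 the gap is zero.

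**Step 5. Scale.** With 49 eyes the sampling standard error is √(0.059 × 0.941/49) = 3.4 points at the lower risk and √(0.143 × 0.857/49) = 5.0 points at the higher. Even at 30% loss, the gaps of 0.9 and 2.1 points are smaller than that.

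**The case against.** Descriptive safety reporting is common in a small carry-over extension whose size was fixed by earlier enrolment. A medical monitor, a data and safety monitoring committee and a Safety Plan are in place. Anyone given 0 of 7 can work out the exact limit. Section 8.4 names who is included but does not state how someone who leaves early is counted, and its wording does not exclude further tables.

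Much of this stands. Having no hypothesis test is not a fault, and the size of the exposure problem depends on losses that the documents do not give. But a reader can derive a limit only from a clear denominator. Eye-time by implant status cannot be recovered from a frequency table at all.

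Three stronger readings are tempting, and the documents support none of them:
- A reader might infer that risk is bound to be understated. That needs losses and a denominator that keeps those who leave; with complete follow-up the shortfall is zero.
- A reader might run the calculation over six years from surgery, which gives 9.7% against 11.4% and 22.7% against 26.5% at 30% loss. Adverse events are captured only from extension consent, so that window is too long and roughly doubles the gap.
- A reader might infer that the protocol treats zero events as proof of safety, pointing to the Précis: "We found the implanting of the NT-501 was safe as demonstrated by the ERG findings". That sentence rests on ERG and visual function in the Phase 1 study, not on an event count. No section says that zero events means safe.

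**Conclusion.** The point holds as a gap in a stated method. Safety is half of the first objective, its analysis has neither interval nor time at risk, and the protocol's own rules make exposure unequal. Giving Cohort 1 dichotomous efficacy outcomes a 95% interval while giving safety outcomes in the same 7 participants none is inconsistent.

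The missing interval is the larger part and does not depend on dropout. The 41% limit for Cohort 1 uses only the stated 7 eyes; the Cohort 2 limit of about 7% rests on the assumed 49 implanted eyes. The understatement from early leaving is conditional and modest: up to about 2 points under the assumed risks at 30% loss, and nil without loss. These figures assume a constant risk and loss unrelated to it.

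**What to change.** In Section 8.4, keep the tabulation and replace the sentence ruling out formal analysis with a statement that no hypothesis tests will be made. For each Section 6.1.3 outcome and for serious adverse events, add:

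- **(a)** the number and percent with an exact 95% interval, including for zero counts;
- **(b)** events per eye-year (ocular) or person-year (non-ocular) at risk with an exact Poisson 95% interval. Count risk time from extension consent, assign eye-time to implant in place, sham or untreated, or after explant, and report Cohort 2 implant and sham eyes separately;
- **(c)** cumulative incidence at the annual visits where counts allow, with the time origin stated: extension consent, or surgery with delayed entry.

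Use participant-level or cluster-adjusted intervals wherever both eyes of a participant contribute.

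The cost is a few table columns and the derivation of eye-time from consent, surgery, explant, event and last-visit dates. The intervals will be wide and the stated safety figures slightly less favourable.

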8.5 Adverse Events

Adverse events will be tabulated by body system, high-level term and preferred term separately for each Cohort. Summaries of adverse events by severity will be provided. Separate summaries will be prepared for non-ocular and ocular adverse events, with events in the study eye(s) and fellow eye summarized separately for Cohort 1 and 2. Separate summaries of non-

ocular and ocular adverse events reported as related to the implant or the implant surgery will be prepared. Serious adverse events will be summarized similarly. Adverse events leading to discontinuation from the study will be listed and tabulated.

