Participant visits will occur at Months 72, 84, 96 and 108 (+/- 1 month) following the date of the surgical procedure for NTMT-01.

Cohort 2 - Prospective, multi-center, single-masked sham-controlled study. All participants will have been enrolled (undergone a NT-501 implant and/or sham procedure) in the *A Phase 2 Multicenter Randomized Clinical Trial of Ciliary Neurotrophic Factor (CNTF) for Macular Telangiectasia Type 2 (MacTel NTMT-02)* protocol and have agreed to continue in this follow-up study.

In the event that the NTMT-02 study is positive, Cohort 2 participants who received sham only may be eligible for active treatment in the control/non-treated eye.

Participant visits will occur at Months 36, 48, 60 and 72 (+/- 1 month) following the date of the surgical procedure for NTMT-02.

Sample Size:

Cohort 1 - 7 participants (7 study eyes) – previously enrolled in NTMT-01 protocol

Cohort 2 – 66 participants (98 study eyes) – previously enrolled in NTMT-02 protocol

Diagnosis and Key Eligibility Criteria: Previously enrolled in NTMT-01 or NTMT-02 protocols

Investigational Product: NT-501 implant

Duration of Treatment:

Cohort 1 - Visits to continue until Month 108 from date of study procedure, with annual analyses at Months 72, 84, 96, and 108.

Cohort 2 - Visits to continue until Month 72 from date of study procedure, with annual analyses at Months 36, 48, 60, and 72.

Number of Centers: 8 sites in the United States and 3 sites in Australia

Study Outcomes:

Cohort 1: The following efficacy outcomes as outlined in the NTMT-01 Protocol will continue to be analyzed to investigate the efficacy of Ciliary Neurotrophic Factor (CNTF) produced by NT-501 (all changes relative to NTMT-01 baseline measurements):

- Change in the ellipsoid zone (area of IS/OS loss) from baseline to Months 72, 84, 96 and 108.
- Change in retinal sensitivity (dB) as measured by microperimetry from baseline to Months 72, 84, 96 and 108.
- Proportion of study eyes with a 35% or more increase from baseline in the ellipsoid zone (area of IS/OS loss) at Months 72, 84, 96 and 108.
- Change in best corrected visual acuity (BCVA) from baseline to Months 72, 84, 96 and 108.
- Proportion of study eyes with 15 or more letter loss from baseline in BCVA at Months 72, 84, 96 and 108.
- Proportion of study eyes with 10 or more letter loss from baseline in BCVA at Months 72, 84, 96 and 108.

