6.1.3 Safety Outcomes

The following ocular events (regardless of attribution) will be considered safety outcomes for both Cohorts if they occur:

- Rejection or extrusion of the NT-501 device.
- Development of peri-implant fibrosis, which either blocks the visual axis of the implanted eye or affects the lens or retina (minor/moderate fibrosis around the implant and/or the attachment point is an expected possibility and will be considered safe on ocular function). Attention should focus on fibrosis that may detach the retina.
- Development of choroidal or retinal neovascularization in the study eye.
- Adverse events affecting ocular function, which are different from those expected in the normal course of MacTel, which are potentially related to the surgical procedure, implant or CNTF including:
 - Endophthalmitis
 - Vitreal inflammation
 - Tractional retinal detachment

- Sectorial lens opacification
- Intraocular hemorrhage
- High or low Intraocular pressures
- Dry eye
- Self-reported change in dark adaptation
- Miosis
- Persistent chemosis
- Scleral leak

All adverse events (AEs) will be captured from the date of the Extension Study Consent whether or not considered to be related to the surgical procedure, NT-501 device, or CNTF. All adverse events occurring between the final NTMT-01 or NTMT-02 study visit will be considered part of the participants' Medical and/or Ophthalmic History.

An attempt will be made to differentiate between treatment-related AEs and AEs considered to be part of the normal progression of the disease. In addition, for treatment-related AEs, an attempt will be made to differentiate those the Investigator believes are due to the procedure, NT-501 device, or CNTF.

Analysis of safety events will be conducted separately for each Cohort.

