6.7 Masking

For participants in Cohort 2 there are different levels of masking within the study. The site staff refractionist, visual acuity examiner and photographers/imagers must remain masked to treatment assignment (NT-501 implant or sham procedure) for all visits. The Ophthalmologist, Surgeon and Clinic Coordinator will be unmasked to treatment assignment.

To ensure that the refractionist, visual acuity examiner and photographers/imagers remain masked to the randomized assignment, the Ophthalmologist, Surgeon and Clinic Coordinator are not to discuss the treatment received with the refractionist, visual acuity examiner and photographers/imagers.

All personnel in the Central Image Reading Center will be masked to whether the participant received the NT-501 implant or sham in a study eye(s).

Masking will remain as described above until all 66 participants in the NTMT-02 protocol have completed their original NTMT-02 Protocol Month 24 visit and data analysis has been completed. At that time, the Principal Investigators will be informed by the Sponsor that they

may unmask the participants. They may choose to do this at the participants' next scheduled visit or in a personalized communication to the participant. The sites will notify the Coordinating Center of the unmasking as outlined in the Manual of Procedures.

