7.8 Notifying FDA / Regulatory Authorities and the Data and Safety Monitoring Committee

After the SAE has been reported by the Principal Investigator and assessed by the IND Sponsor, the IND Sponsor or their designee must report the event to the appropriate regulatory authorities using one of these two options:

- Standard reporting (report in the annual report). This option applies if the AE is classified as one of the following:
 1. Serious, expected, suspected adverse reaction (serious, expected and related)
 2. Serious and not a suspected adverse reaction (serious and not related)
- Expedited reporting is required. This option applies if the AE is classified serious and unexpected suspected adverse reaction (serious, unexpected and related).

The Sponsor must report an adverse event as a suspected adverse reaction (related AE) only if there is evidence to suggest a causal relationship between the test article and the adverse event, such as:

- A single occurrence of an event that is uncommon and known to be strongly associated with test article.
- One or more occurrences of an event that is not commonly associated with the test article exposure, but is otherwise uncommon in the population exposed to the test article.
- Aggregate analysis of specific serious adverse events observed in a clinical trial (such as known consequences of the underlying disease or condition under investigation or other events that commonly occur in the study population independent of the test article therapy) that indicates those events occur more frequently in the test article treatment group than in a concurrent or historical control group.
- Any findings from clinical or epidemiological studies, analysis of data pooled across multiple studies, published or unpublished scientific papers or from animal or in vitro testing that would result in a safety-related change in the protocol, informed consent, General Investigational Plan section of the IND or other aspects of the overall conduct of the trial.

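### Sections 8.4 and 8.5 specify no NT-501 versus sham split for Cohort 2 ocular safety, and the stated study-eye versus fellow-eye grouping mixes the two arms

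*Combined protocol and SAP*

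**What the plan says.** Section 8.5 sets out the adverse event tables. They are produced by cohort, by coded term, by severity, and by ocular versus non-ocular, "with events in the study eye(s) and fellow eye summarized separately for Cohort 1 and 2". Events reported as related to the implant or its surgery get their own summaries, and serious events are handled in the same way.

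Section 8.4 covers adverse events, serious adverse events and the "pre-specified safety outcome as defined in Section 6.1.3 and will include frequency and descriptive tabulation". It rules out formal testing and takes implant and sham recipients together as the safety population. Section 6.1.3 opens its list with "The following ocular events (regardless of attribution) will be considered safety outcomes for both Cohorts if they occur", and on analysis adds only that each cohort is handled separately.

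The Study Summary describes Cohort 2 as sham-controlled, with 66 participants and 98 study eyes. Section 6.7 has reading-center staff masked to whether a study eye received NT-501 or sham. Section 8.2 discusses the case where "paired eyes from the same participant are in different treatment groups" and compares the treatment groups for efficacy. None of the safety-analysis text calls for that comparison.

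**The concern.** One grouping is applied to two different designs. Cohort 1 is open label with 7 participants and 7 study eyes, so study eye versus fellow eye is implanted versus not implanted. In Cohort 2 the same split sets a mixture of NT-501 and sham eyes against eyes that were in neither arm.

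Cohort 2 holds the study's only concurrent sham control, and long-term safety is part of the first objective. The contrast matters most for ocular events that are neither specific to the device nor attributed to it. Neovascularization is an example: Section 6.1.3 lists it as a safety outcome in the study eye, and Section 2 describes it as a feature of progressing MacTel. A study-eye count cannot separate the two explanations, whereas sham study eyes could help.

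The related-event summaries do not fill the gap, because they rest on investigator attribution and "The Ophthalmologist, Surgeon and Clinic Coordinator will be unmasked to treatment assignment".

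**Working it through.** **1. Is the split supplied anywhere?**

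| Section | Grouping given for safety |
|---|---|
| 6.1.3 | By cohort; related events to be attributed to procedure, device or CNTF |
| 7.8 | None; a criterion for judging and reporting relatedness |
| 8.4 | None; descriptive tabulation in all implant or sham recipients |
| 8.5 | Cohort, term, severity, ocular/non-ocular, study/fellow eye, reported as related |
| 8.2 (efficacy) | Compared between treatment groups |

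No safety entry names NT-501 versus sham.

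**2. Eye counts in Cohort 2** (inputs: 66 participants and 98 study eyes, from the Study Summary; one or two study eyes each; upper limits that apply if all 66 enroll)

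- Participants with two study eyes: 98 - 66 = 32
- Participants with one study eye: 66 - 32 = 34 (check: 2 × 32 + 34 = 98)
- Fellow eyes: 2 × 66 - 98 = 34

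The stated split is therefore up to 98 mixed study eyes against up to 34 fellow eyes.

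**3. Illustration of dilution.** The documents give neither the NT-501 share of the 98 eyes nor any event rate, so the following are assumptions:

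- Each of the 32 two-study-eye participants has one eye per arm. Section 8.2 shows that this can occur, not that it always does.
- Of the 34 single study eyes, 0 to 33 are NT-501. At least one is left as sham because Section 5 provides for sham-only participants. NT-501 eyes, nT, then number 32 to 65.
- Event risk is 20% in NT-501 eyes and 5% in sham and fellow eyes, a true difference of 15 points.

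Pooled study-eye risk = (nT × 0.20 + (98 - nT) × 0.05) / 98.

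Study minus fellow = pooled risk - 0.05, which equals (nT / 98) × 15 points.

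| NT-501 / sham eyes | Pooled study-eye risk | Study minus fellow |
|---|---|---|
| 32 / 66 | (6.40 + 3.30) / 98 = 9.9% | 4.9 points |
| 49 / 49 | (9.80 + 2.45) / 98 = 12.5% | 7.5 points |
| 65 / 33 | (13.00 + 1.65) / 98 = 14.9% | 9.9 points |

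Under these assumptions the tabulated contrast recovers between 32/98 = 33% and 65/98 = 66% of the true difference. That share depends on the arm sizes and on fellow eyes carrying the sham-eye risk, not on the 20% and 5% chosen.

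**The case against.** The strongest reply is that Section 8.5 is a short protocol-level summary and that silence is not an instruction to pool. An arm column is compatible with every sentence in Sections 8.4 and 8.5, the cohort is declared sham-controlled, and eye-level treatment is already needed for the Section 8.2 models. No data are lost, so the table could be produced at any time. This stands as far as it goes. The point concerns what the plan commits to, and the one eye-level grouping it does state is unsuited to Cohort 2.

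Three stronger readings are tempting, and the documents do not support them.

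- *That the plan orders pooling of the arms.* It omits the split and does not forbid it.
- *That implant harms in general would be hidden.* Extrusion, peri-implant fibrosis and events attributed to the implant or its surgery remain identifiable, and Sections 6.1.3 and 7.3 ask investigators to attribute related events to procedure, device or CNTF.
- *That Section 7.8 makes these tables the basis for judging all ocular events.* Its aggregate-analysis criterion, that "those events occur more frequently in the test article treatment group than in a concurrent or historical control group", applies to specific serious adverse events and is a sponsor reporting duty. It supports the value of a concurrent contrast for serious events only, and if anything presupposes that the sponsor can compare groups outside the Section 8 tables.

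The Safety Plan (Section 7.1) and DSMC Charter (Section 7.11) are not among the documents. As described, they cover reporting, monitoring and committee operations, not the Section 8 tables.

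**Conclusion.** The point holds as a gap in specification confined to Cohort 2. Tables that follow the stated grouping would not show the study's only concurrent sham contrast for ocular events that are neither device-specific nor attributed to the implant, and a pooled study-eye rate would dilute any implant effect on those events.

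Safety is descriptive, so no test, error rate or decision rule changes. What changes is what a reader of the safety tables can conclude. The size for this trial is unknown: 4.9 to 9.9 points against 15 illustrates the mechanism under assumed risks and arm sizes, and is not an estimate. The gap is worth closing because the stated grouping does not fit the design and the correction is cheap.

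**What to change.** In Sections 8.4 and 8.5, state that Cohort 2 ocular adverse events, ocular serious adverse events and Section 6.1.3 outcomes will be tabulated descriptively by treatment received: NT-501 study eyes, sham study eyes and untreated fellow eyes, with the number of eyes in each column. Keep study eye versus fellow eye for Cohort 1.

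Section 5 leaves open later active treatment of sham-only participants. If any sham or untreated eye is implanted later, classify its events by treatment status at onset, and give eye follow-up time for every affected column, both the original and the post-implant one. For example, between Month 36 and Month 72 an eye implanted at an assumed Month 48 contributes 12 months before and 24 months after, so an eye count alone is not an adequate denominator for either column. Capture the implant date in the analysis database: Section 6.5 requires ocular procedures in a source document, which does not by itself guarantee that.

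The cost is a few sentences, a few more descriptive tables, some with small cells, and one date field if it is not already captured. No formal test is added.
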